10.2 Secondary study parameter(s)

Tumor-to-background ratios and tumor-to-'healthy salivary gland tissue' ratios will be calculated using the SUV. It will be presented as mean and standard deviations.

Immunohistochemical PSMA expression on a tissue sample of the primary tumor will be quantified using a four point scale for tumor PSMA expression (0 = no expression, 1 = weak expression, 2 = moderate expression, and 3 = strong expression) and the number of PSMA-positive blood vessels per mm² will be counted.

The correlation between the immunohistochemical PSMA expression and tumor SUV will be evaluated using linear regression analysis. A p-value of <0.05 will be considered significant. Analyses will be performed using SPSS version 22.0.

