4.4 Sample size calculation

The main purpose of this study is to establish the feasibility and value of ⁶⁸Ga-PSMA-PET/CT scans as a non-invasive method to assess PSMA expression in ACC/SDC patients. An exact sample size calculation is not applicable, because baseline information concerning the uptake of ⁶⁸Ga-PSMA in ACC/SDC patients is not available. Therefore we will establish ⁶⁸Ga-PSMA-PET/CT scanning in 15 ACC and 10 SDC patients. If the technique does not prove its value in these patients, we will conclude that it is not a valuable imaging technique for ACC/SDC patients.

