8. METHODS

8.1 Study parameters/endpoints

8.1.1 Main study parameter/endpoint

The SUV of ⁶⁸Ga-PSMA estimated with ⁶⁸GA-PSMA-PET scanning. If the SUV of tumor tissue is higher than the SUV of healthy salivary gland tissue and/or comparable to the SUV in prostate cancer, the level of PSMA expression is deemed high enough to pursue a therapeutic study with ¹⁷⁷Lu-PSMA.

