10. STATISTICAL ANALYSIS

10.1 Primary study parameter(s)

SUV will be calculated according to the following formula:

(measured activity concentration [MBq/mL] * body weight [g]) / injected activity [MBq]

The PET/CT images will be reconstructed in three dimensions. The PET and CT images will be fused and the SUVs will be aligned with CT to assess ⁶⁸Ga-PSMA uptake in tumor lesions, healthy salivary gland tissue, and the background.

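### The tumor-to-gland ratio is summarised only as arithmetic mean and SD, so with right-skewed ratios the mean can exceed 1 while most patients' tumors take up less than the gland

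*Combined protocol and SAP*

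**What the plan says.** - **Ratios (section 10.2).** Tumor-to-background and tumor-to-gland "ratios will be calculated using the SUV", and "It will be presented as mean and standard deviations". No median, range, log scale, confidence interval, count of patients above 1 or split by tumor type is planned. The unit, patient or lesion, is not stated.
- **Primary SUV (section 10.1).** "SUV will be calculated according to the following formula", followed by image reconstruction and fusion. No summary statistic is given.
- **Criterion for a therapeutic study (section 8.1.1).** "If the SUV of tumor tissue is higher than the SUV of healthy salivary gland tissue and/or comparable to the SUV in prostate cancer", expression counts as high enough. No statistic and no share of patients is attached to either limb.
- **Size and spread (section 4.4).** The plan is "scanning in 15 ACC and 10 SDC patients". It gives no variance: "An exact sample size calculation is not applicable, because baseline information concerning the uptake of" the tracer in these tumors is lacking.
- **Significance level (section 10.2).** "A p-value of <0.05 will be considered significant" belongs to the regression of SUV on immunohistochemistry and does not apply to the ratios.

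**The concern.** The first limb of the section 8.1.1 criterion, "If the SUV of tumor tissue is higher than the SUV of healthy salivary gland tissue", is the same as a tumor-to-gland ratio above 1. Since 10.1 plans no summary of the SUV itself, the mean ratio in 10.2 is the only planned number that a reader can hold against that limb.

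An arithmetic mean suits this comparison poorly. A ratio cannot fall below 0 but has no upper limit, so in a group of 10 or 15 a few high-uptake patients can pull the mean above 1. The study is meant to show whether these patients could be candidates for the radionuclide treatment. How many of them exceed the gland is therefore central, and a mean with an SD does not show it. The SD describes spread between patients and is not itself an interval for the estimate.

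**Working it through.** The plan has no power figure or expected ratio to reproduce.

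**Inputs.** From the documents: 15 ACC and 10 SDC patients (4.4), mean and SD as the summary (10.2), and 1 as the value that matters for the gland ratio (8.1.1). Assumed, because the documents give nothing: log-normal ratios, true median 0.8 or 0.9, and log-scale SD *s* from 0.3 to 0.9.

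**1. Asymmetry, with no distribution assumed.** Five patients at 0.5 and five at 2.0 give (5 × 0.5 + 5 × 2.0)/10 = 1.25 for tumor/gland. Inverting every ratio gives the same ten values, so gland/tumor also averages 1.25. The geometric mean is 1.0 both ways.

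**2. A few high values, n = 15.** Ten patients at 0.5 and five at 2.5:
- arithmetic mean (5 + 12.5)/15 = 1.17, SD 0.98
- geometric mean exp[(10 ln 0.5 + 5 ln 2.5)/15] = 0.85; median 0.5
- patients below 1: 10/15 = 67%

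**3. Size under a log-normal.** Mean/median = exp(s²/2). If the true mean is exactly 1, the median is exp(−s²/2) and the share of patients below 1 is Φ(s/2).

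| s | mean/median | median when mean = 1 | share below 1 when mean = 1 |
|---|---|---|---|
| 0.3 | 1.046 | 0.96 | 56% |
| 0.5 | 1.133 | 0.88 | 60% |
| 0.7 | 1.278 | 0.78 | 64% |
| 0.9 | 1.499 | 0.67 | 67% |

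**4. How often the summary and the majority disagree.** The event is that the average exceeds 1 while fewer than half of the sampled patients do. Simulation with at least 200,000 studies per setting, n = 15:

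| s | median 0.8: arithmetic | median 0.8: geometric | median 0.9: arithmetic | median 0.9: geometric |
|---|---|---|---|---|
| 0.3 | 0.7% | 0.1% | 11% | 2.5% |
| 0.5 | 15% | 1.3% | 29% | 5.4% |
| 0.7 | 35% | 3.1% | 41% | 6.9% |
| 0.9 | 48% | 4.5% | 48% | 7.7% |

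At n = 10, not counting 5/5 splits, the arithmetic mean gives about 1% to 29% over the same *s* range at median 0.8, and 7% to 28% at median 0.9. With the sample median as the summary, the event cannot occur at n = 15.

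**5. A different event.** The chance that the arithmetic mean exceeds 1 at all is larger: 72% at n = 15, median 0.9, s = 0.7, against 28% for the geometric mean. That count includes studies in which most sampled patients do exceed 1. The true mean there is 0.9 × exp(0.245) = 1.15, so a mean above 1 is a correct estimate of the mean. The table in step 4 is the relevant one.

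**The case against.** The strongest reply is that section 8.1.1 does not use the mean ratio. The ratios are secondary endpoints, the criterion names no statistic, and its second limb, comparability with prostate cancer, is untouched by a gland ratio. This stands. A reader might infer that the plan tests its go rule with the mean ratio and so leans towards go; the documents do not say so. What remains is that no other planned summary bears on the gland limb.

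A reader might also infer that the mean is biased upward. It is not: it is unbiased for the population mean ratio. It is never below the geometric mean, but under right skew, not in general, it lies above the typical patient. Ten patients at 1.1 and five at 0.2 give (11 + 1)/15 = 0.80 although 67% exceed 1. Right skew is plausible for a positive ratio, but the documents contain no data to show it.

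The spread is assumed too, and the medians examined lie just below 1, where disagreement is easiest to see. At log-SD 0.3 and median 0.8 the problem nearly vanishes.

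Finally, mean and SD is a legitimate description in an exploratory study of 25 patients, and nothing forbids reporting counts as well. That is fair, but nothing commits the investigators to do so, and unknown spread is a reason to fix a robust summary in advance.

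**Conclusion.** The point holds in a limited form. Mean and SD, the only planned summary of the tumor-to-gland ratio, can show an average above 1 when most patients' tumors take up less than the gland. At n = 15 the chance runs from 0.7% to 48% for log-SD 0.3 to 0.9 at median 0.8, and from 11% to 48% at median 0.9; the geometric mean keeps it at or below 7.7% throughout. These figures rest on log-normal ratios, one value per patient, and a spread and median that the documents do not supply.

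The consequence is a risk of misreading the gland limb of 8.1.1. The documents do not support the stronger claim that a wrong go decision follows. Nor does the point carry over to tumor-to-background in the same form, because no threshold of 1 is given for that ratio. The change is worth making, mainly because it is nearly free.

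**What to change.** **Section 10.2.** Define one tumor-to-gland ratio per patient. Report, separately for ACC and SDC:
- the geometric mean with 95% CI, calculated on the log scale, or the median and range;
- the number of patients with a ratio above 1, with an exact 95% CI.

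The mean and SD may stay alongside.

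**Sections 10.1 and 10.2.** Summarise tumor SUV and the tumor-to-background ratio on the log scale as well, without a threshold of 1.

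**Section 8.1.1.** State which of these summaries the gland limb of the criterion uses.

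**Cost.** A few sentences of plan text and minutes of analysis, with no extra patients, scans or data. The headline average will usually be lower than the arithmetic mean, and a log-scale summary needs every ratio to be positive.

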1. INTRODUCTION AND RATIONALE

PSMA is a transmembrane protein. PSMA expression can be visualized and quantified by immunohistochemical staining of tissue biopsies with anti-PSMA monoclonal antibodies.¹ This has been done for numerous healthy and malignant tissues. PSMA expression appears to be restricted to a few healthy tissues, such as the prostate, duodenum, proximal renal tubules, breast and skeletal muscle.² Results on PSMA expression of healthy salivary gland tissue are conflicting.¹⁻⁴ In malignant tissue, PSMA expression was found in prostate cancer cells and the neovasculature of many other solid malignancies, including renal cell carcinoma, bladder cancer, colon cancer, neuroendocrine carcinoma, melanoma, pancreatic cancer, non-small cell lung cancer, breast cancer and others.² In ACC, a study in 54 patients showed PSMA expression in 85% of patients, and in 70% of patients with recurrent ACC.⁵ The level of PSMA expression in SDC is currently under investigation, and the first results show PSMA expression in >80% of patients.

PSMA expression is of increasing importance, as it is a target for cancer diagnostics. After labelling PSMA ligands with ⁶⁸Ga, PSMA expression can be visualized non-invasively with a ⁶⁸Ga-PSMA-PET/CT scan. In a study in 248 patients with a history of prostate cancer who presented with a rising PSA level, it was found that ⁶⁸Ga-PSMA-PET/CT scans visualized substantially more tumor lesions than reported for other imaging modalities, such as CT, ¹⁸F-FDG-PET (figure 1), ¹¹C-choline-PET and MRI.⁶ This demonstrates that radiolabeled PSMA ligands very effectively target prostate cancer lesions in vivo, allowing specific and sensitive detection of prostate cancer lesions with PET.

[figure not shown]

Figure 1. ¹⁸F-FDG-PET scan (left) and ⁶⁸Ga-PSMA-PET scan (right) in a patient with metastatic prostate cancer. The black dots in the abdomen on the right scan represent prostate cancer metastases that could not be visualized by ¹⁸F-FDG-PET.

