4.2 Inclusion criteria

In order to be eligible to participate in this study, a subject must meet all of the following criteria:

- locally advanced, recurrent or metastatic ACC/SDC
- Age \geq 18 years old
- Ability to provide written informed consent

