8.1.2 Secondary study parameters/endpoints

- the SUV tumor-to-background ratio
- the SUV tumor-to-‘healthy salivary gland tissue’ ratio.
- The correlation between the SUV and the degree of immunohistochemical PSMA expression of the primary tumor on archival tissue.
- The establishment of new metastatic lesions.

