8.5 Replacement of individual subjects after withdrawal

If a subject decides to withdraw, another patient will be recruited until 15 ACC and 10 SDC patients have completed the study protocol.

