In ACC and SDC, the investigational product has not been evaluated before and is therefore not yet predictable. In this study we will correlate the SUV of the primary tumor with the level of immunohistochemical PSMA staining on archival tissue to establish whether the efficacy of PSMA-PET imaging can be predicted with immunohistochemistry.

j. Can effects be managed?

No side effects which require to be managed have been reported in the literature. However, if a participant develops unexpected side-effects, the study center (Radboudumc) can deliver adequate medical support of emergencies.

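### Section 10.2 relates SUV to PSMA staining across two tumour types with no histology term; adding one is a cheap, minor improvement

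*Combined protocol and SAP*

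**What the plan says.** Section 10.2 gives the whole model in one sentence: "The correlation between the immunohistochemical PSMA expression and tumor SUV will be evaluated using linear regression analysis". The threshold is p<0.05. The text names no covariate, and it neither says that the two tumour types are pooled nor rules out adjustment. One fit of SUV on staining across all patients is the plain reading.

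The sample is set by tumour type. Section 4.4 plans "scanning in 15 ACC and 10 SDC patients", and section 8.5 replaces withdrawals: "another patient will be recruited until 15 ACC and 10 SDC patients have completed the study protocol".

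Section 10.2 defines two staining measures, a 0–3 score for tumour cells and a count of PSMA-positive vessels per mm². It does not say which one is the main predictor.

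The SUV to be used is described in different ways. Section 10.2 refers to tumour SUV generally. Section 8.1.2 lists "The correlation between the SUV and the degree of immunohistochemical PSMA expression of the primary tumor on archival tissue", which ties only the staining to the primary. Section 13.1 (item i) says "we will correlate the SUV of the primary tumor with the level of immunohistochemical PSMA staining on archival tissue". Eligibility under section 4.2 is "locally advanced, recurrent or metastatic ACC/SDC".

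On differences between the tumour types, section 1 reports for ACC that "a study in 54 patients showed PSMA expression in 85% of patients, and in 70% of patients with recurrent ACC", and for SDC that "the first results show PSMA expression in >80% of patients". Section 4.4 says that no baseline uptake data exist.

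**The concern.** ACC and SDC are different tumours, enrolled in fixed numbers, and tumour type is known for every patient. Leaving it out of the regression can do two kinds of harm.

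- If SUV differs by tumour type, the difference goes into the residual and the slope is estimated less precisely.
- If staining scores differ as well, part of the ACC–SDC contrast is attributed to staining. A slope can then appear with no relation inside either tumour.

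Section 13.1 uses this analysis to judge whether staining can predict how well PSMA-PET imaging works. For that purpose the relation within a tumour type is what counts. With 25 patients and no plan to enlarge the sample, the choice of model is one of the few ways to improve the answer.

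**Working it through.** **Inputs.** From the documents: 15 ACC, 10 SDC, linear regression, p<0.05 (taken as two-sided). Everything else is assumed. Unless stated, SUV is log-normal with residual log-SD 0.7, SUV rises 0.4 log units per score step, and scores 0/1/2/3 occur in 15/20/30/35% of both tumour types. The plan gives no power or effect size for this analysis, so there is no figure to reproduce.

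**1. Precision lost by omitting histology.** The variance of the tumour-type indicator is (15/25) × (10/25) = 0.24. A two-fold SUV difference is ln 2 = 0.693, which adds 0.24 × 0.693² = 0.115 to a residual variance of 0.7² = 0.49. The standard error of the slope grows by √(0.605/0.49) = 1.11.

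**2. Price of the term when it is not needed.** If score and histology are unrelated, chance alone gives an average R² of 1/24 between them. The variance inflates by about 24/23 = 1.043 and the standard error by about 1.02. Break-even is where 0.24γ²/0.49 = 1/23, so γ = 0.298, or about a 1.35-fold SUV difference.

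**3. Simulated power, without → with histology.**

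| Assumed scenario | Raw SUV | Log SUV |
|---|---|---|
| Log-SD 0.7, 0.4 per step, no ACC–SDC difference | 64 → 61% | 80 → 78% |
| Same, 1.5-fold | – | 76–77 → 77–78% |
| Same, 2-fold | 51–54 → 57–59% | 71 → 78% |
| Log-SD 0.4, 0.2 per step, 1.5-fold | – | 60 → 67% |
| Log-SD 0.5, 0.3 per step, 2-fold* | 53 → 65% | 59 → 75% |
| Log-SD 0.9, 0.3 per step, 2-fold* | 21 → 22% | 30 → 33% |
| Normal errors SD 3, 1.5 SUV units per step, no difference* | 61 → 59% | 59 → 57% |
| Same, SDC 3 SUV units lower* | 53 → 60% | 49 → 55% |

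*Score mix 15/30/35/20%. At log-SD 0.4 and a 2-fold difference the gain on the log scale is about 20 points. The last two rows show that the benefit of the term does not depend on SUV being log-normal.

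**4. False positives when both differ.** Suppose there is no true relation, SDC scores are 20/40/30/10%, and SDC SUV is half that of ACC. This mix makes 80% of SDC positive, at the edge of the reported figure.

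- Mean scores are 1.85 (ACC) and 1.30 (SDC), a difference of 0.55.
- The total score variance is 0.6 × 1.1275 + 0.4 × 0.81 + 0.24 × 0.55² = 1.073.
- The spurious pooled slope is 0.24 × 0.55 × 0.693/1.073 = 0.085 log units per step, an apparent 9% rise in SUV per step.
- Simulated false-positive rates over log-SD 0.4–1.0 are 6–12% for pooled raw SUV, 7–13% for pooled log SUV, and about 5% for log SUV with histology.
- With identical score mixes there is no inflation (4–5%).

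**5. Further costs of adjusting.** If score mixes differ as in step 4 but SUV does not, power on the log scale falls from 78% to 73%. At an R² of 0.3 between score and histology it falls from 82% to 67%. The model also assumes one slope. If the relation exists only in ACC (0.5 against 0 per step), log SUV with histology estimates an average of about 0.30 that fits neither tumour. Its power is then 50%, against 36% for pooled raw SUV. A test of the slope difference has only 38% power.

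**6. Which SUV and which staining measure.** Section 13.1 needs the primary tumour's SUV. Section 4.2 admits recurrent and metastatic disease, section 8.1.3 records past surgery, and section 10.1 measures lesions in the plural. Some patients may therefore have no primary at the scan, and others several lesions. If staining tracks the primary but another lesion is measured, an adjusted power of 78% becomes 72%, 61% or 50% at an assumed between-lesion log-SD of 0.3, 0.5 or 0.7. If both staining measures were tested at 0.05, the chance of at least one false positive would be 1 − 0.95² = 9.75% if they were independent.

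**The case against.** The strongest defence is that section 10.2 is brief but usable. A simple regression is a legitimate exploratory analysis, the wording does not forbid a covariate, and nothing in the documents shows that ACC and SDC differ. Staining positivity is 85% against more than 80%, and there are no uptake data. On that evidence the histology term might only cost power. This largely stands: the plan contains no error here, and the gain cannot be claimed as a fact. It does not remove the case for the term, because the likely loss is small and the possible loss without it is larger.

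Four stronger readings are tempting and not supported.

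- A reader might infer that the planned result will be confounded. That needs differences in both staining and SUV, and the documents show neither.
- A reader might set the 70% positivity in recurrent ACC against the SDC figure. The SDC figure is preliminary and not split by stage. Positivity also says nothing about how scores 1 to 3 are distributed.
- A reader might treat log SUV and histology as one necessary package. They are separate choices. Logging alone leaves the confounding in place, and its advantage depends on skewed SUV. With additive normal errors and no tumour-type difference, pooled raw SUV has about 78% power against about 74% for log SUV with histology.
- A reader might think the go/no-go decision is affected. Section 8.1.1 compares tumour SUV with salivary gland and prostate cancer values and does not use this regression.

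**Conclusion.** The point holds as a minor, low-cost improvement. A pooled fit without tumour type is the plain reading of section 10.2. A histology covariate is the better method whether or not SUV is logged. At a two-fold SUV difference the term is worth about 7 to 20 points of power on the log scale at log-SD 0.7 or below, and about 3 points at 0.9. It loses about 2 points if histology is irrelevant. It also holds false positives near 5% where the pooled fit can reach 12–13%. All of these sizes rest on assumed SUV spread, score mixes and tumour-type differences.

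The unclear choice of SUV and of staining measure is a wording gap that the same edit should close. The correlation is secondary in sections 2 and 8.1.2, although the Summary lists it among the main endpoints.

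**What to change.** In section 10.2, before the analysis:

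1. Keep linear regression and add histology (ACC or SDC) as a covariate. Report the adjusted slope per score step with its 95% CI.
2. Plot ACC and SDC separately as a rough check of the common slope.
3. State the SUV scale. Log SUV is reasonable but optional; if it is used, give untransformed or rank-based results as a sensitivity check.
4. Define one SUV per patient, reconcile sections 10.2 and 13.1, and give a rule for patients whose primary is no longer present.
5. Say whether the 0–3 score or the vessel count is the main predictor.

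This takes a few lines, the same SPSS procedure and no extra patients. The statistical price is one degree of freedom, the power losses in steps 2, 3 and 5 of the working, and reliance on a common slope that 25 patients can check only roughly.

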10.3 Other study parameters

Background variable will be described using simple descriptive statistics and will be presented in a table. Missing data will be mentioned in the final manuscript.

10.4 Interim analysis

Not applicable

11. ETHICAL CONSIDERATIONS

11.1 Regulation statement

The study will be conducted according to the principles of the Declaration of Helsinki (version 8, 19 October 2013), in accordance with the Medical Research Involving Human Subjects Act (WMO), the personal data protection act (Wet Bescherming Persoonsgegevens), and the Medical Treatment Agreement Act (WGBO).

11.2 Recruitment and consent

Patients will be informed about the study by their treating physician during normal patient care. Detailed information about the study can be offered by the investigators during normal patient care or by phone call. If a patient decides to participate, a screening visit will be planned, which starts with signing the IC. At least 24 hours will be taken into account between informing patients about the study and signing the IC.

11.3 Objection by minors or incapacitated subjects

Not applicable

11.4 Benefits and risks assessment, group relatedness

Risk assessment: as ^{68}Ga -PSMA-PET/CT imaging is a known diagnostic procedure used for prostate cancer in normal patient care, the risks of this procedure are well known and minimal. Next to this, 30 ml blood will be drawn from the participants by a venapuncture. This risks of this procedure are also well known and minimal.

Benefit assessment: participants will not benefit directly from this study as it is a non-therapeutic trial. If the study is successful, participants may participate in a therapeutic study with ^{177}Lu -PSMA which may be beneficial.

Group relatedness: the study does not involve minors and/or incapacitated subjects

